5.1.2 Subject Exclusion Criteria

- History of other prior malignancy, with the exception of curatively treated basal cell or squamous cell carcinoma of the skin, cervical cancer stage IB and stage I prostate cancer considered not necessary to treat
- Disease suitable for curative salvage surgery
- Treatment with any investigational medicinal product (IMP) that may interfere with the study treatment, within 4 weeks prior to first administration of study drug.

- Significant cardiac, pulmonary or other medical illness that would limit activity or survival
- Pregnancy or lactation.
- Known hypersensitivity to any of the components of the investigational product
- Patients who test positive for hepatitis B, C or HIV.
- Diagnosis of immunodeficiency or medical condition requiring systemic steroids or other forms of immunosuppressive therapy
- Autoimmune disease that has required systemic therapy within the past 2 years
- Any reason why, in the opinion of the investigator, the patient should not participate

5.2 Study treatment

The study will include 20 patients. The following treatment will be used:

- Radiotherapy (RT) to a total dose of 60 Gy, given as 1.5 Gy fractions twice daily for a total period of 4 weeks, will be delivered to the target volumes determined by PET-CT scan. Definition of target volumes and organs at risk will follow the Dahanca guidelines 2013 (published on www.dahanca.dk). The dose delivered to organs at risk, determined by PET-CT scan, will also be calculated.
- Nivolumab administered intravenous every two weeks, starting two weeks (Cycle 1, Day 1) before start of radiotherapy. Nivolumab will be given for a maximum of 12 months or until disease progression.
- Nivolumab will be administered according to a dose escalation schedule (1.0 and 3.0 mg/kg), as shown in Figure 1. Three patients will be included at each dose level. During the dose escalation part the subsequent patient will start therapy with nivolumab 6 weeks after the previous to allow time to observe the possibility for acute toxicity. If no dose limiting toxicity (DLT) is observed at the first dose level, additional three patients will be included at the next dose level. If DLT is experienced see section 8.8 for details. The remaining patients will be treated at the maximum tolerated dose.
- The nivolumab dose will be adjusted to 3.0 mg/kg (standard dose used in NCT02105636) for all patients from Cycle 5, Day 1 (2 weeks after end of radiotherapy), irrespective of starting dose.

The study treatment is outlined in Table 1. Trial treatment should begin within 28 days of first interventional screening assessments. Details on preparation and administration of nivolumab are provided in the IB.

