2.3 Rationale for Dose Selection

Nivolumab is safe and well tolerated up to 10 mg/kg Q2W dose level (see IB). The RT given in the present study gives considerable side effects, related to inflammation that may be enhanced by PD1 blockade. Nivolumab has shown efficacy and mild toxicity when given as monotherapy for HNSCC at a dose of 3.0 mg/kg Q2W, which is the target dose in the present trial(3). To assess the toxicity, the following dosing schedule has been chosen: Nivolumab, intravenous every 2nd week (1 cycle = 2 weeks), dose escalation schedule (1.0, 3.0 mg/kg), for a maximum of 12 months or until disease progression. RT will be given to a total dose of 60 Gy (1.5 Gy fractions twice daily) for a total period of 4 weeks. We expect that any increased toxicity will be observed within 2 weeks after end of RT and thus allow for a 3.0 mg/kg Q2W dose level thereafter. If a drug-related toxicity is observed, the guidelines outlined below will apply.

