3.0 SAFETY MONITORING COMMITTEE

A safety monitoring committee (SMC) will monitor safety on a periodic basis. Members of the

SMC will be experienced clinicians. The SMC will meet approximately every 6 months from the point of first patient in (FPI) to review safety and study conduct data. The safety data will include demographic data, adverse events and relevant laboratory data. In addition the SMC will meet after finalization of each dose cohort (i.e. three patients has completed minimum 8 weeks of treatment), and in case DLT is experienced. See section 8.8 for definitions.

Following each data review, the SMC will provide recommendations to the Study Leadership as to whether the study should continue or be amended, or whether the study should be stopped on the basis of safety (i.e., evidence of harm). The Study Leadership will make a decision on the basis of the SMC recommendations.

Any outcomes of these safety reviews that affect study conduct will be communicated in a timely manner to the investigators for notification of the Institutional Review Boards/Ethics Committees (IRBs/ECs).

No interim efficacy analysis is planned.

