5.2.1 Study drug

The product storage manager at the local pharmacy should ensure that the study drug is stored in accordance with the environmental conditions (temperature, light, and humidity) as determined by BMS. If concerns regarding the quality or appearance of the study drug arise, the study drug should not be dispensed and contact BMS immediately.

Investigational product documentation must be maintained. That includes all processes required to ensure drug is accurately administered. This includes documentation of drug storage,

administration and, as applicable, storage temperatures, reconstitution, and use of required processes (eg, required diluents, administration sets).

Infusion-related supplies (eg, IV bags, in-line filters, 0.9% sodium chloride injection, 5% dextrose injection) will not be supplied by the sponsor and should be purchased locally if permitted by local regulations.

The investigational product should be stored in a secure area according to local regulations. It is the responsibility of the investigator to ensure that investigational product is only dispensed to study subjects. The investigational product must be dispensed only from official study sites by authorized personnel according to local regulations.

[figure not shown]
Please refer to the current version of the Investigator Brochure (IB) and/or pharmacy reference sheets for complete storage, handling, dispensing, and infusion information for nivolumab.

The infusion will be administered by nurses with experience in treatment with immunotherapy.

Table 1 Study Treatment

Drug	Dose/Potency	Dose Frequency	Route of Administration	Regimen/Treatment Period	Use
Nivolumab	1,0 mg/kg	Q2W	IV infusion	Day 1 of each 2 week cycle	Experimental, Dose level 1
Nivolumab	3,0 mg/kg	Q2W	IV infusion	Day 1 of each 2 week cycle	Experimental, Dose level 2
Radiotherapy	1,5 Gy	BID		5 days a week, 4 weeks (Cycle 2 and 3)	Standard

Figure 1

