9.8 Dose Limited Toxicity (DLT)

We foresee that DLT related to Grade 3 and/or 4 dermatitis and mucositis may be experienced.

During dose escalation phase: If a patient experience a possibly nivolumab-related Grade 3 adverse event at any dose level, an additional patient will be included at this dose level. If one more patient experience the same Grade 3 event on the same dose level (i.e. 2 of 4 patients at one dose level experiences the same Grade 3 event), this will be defined as DLT reached, and the dose should be reduced by one level. If DLT is experienced at the lowest dose level (1,0 mg/kg), the dose will be reduced to 0.3 mg/kg. If two patients experience DLT at this dose level, the study will be terminated. If a patient experiences a Grade 4 event, the dose should immediately be reduced by one level.

The Safety Monitoring Committee (SMC) will meet in the case of DLT, to discuss further progress related to doses of nivolumab, and whether the protocol should be amended. In

addition, the SMC will meet after every time three patients have completed each dose level (i.e. completed the re-radiation), to discuss whether it will be safe to move to next dose level. No further patients will be included until the SMC has met. After the dose escalation phase has been completed, the SMC will meet if two patients experience AE grade 3 or one patient experiences AE Grade 4, considered related to nivolumab. No further patients will be included until the SMC has met.

The SMC is a group of oncologists located at the Clinical Cancer Research Unit, with experience in immunotherapy treatment. The members will not be involved in the study design or the study treatment.

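### Sections 3.0 and 9.8 set different triggers for the safety review that clears a dose level, and the 9.8 trigger can come before the third patient's 2 post-radiotherapy weeks are observed

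*Combined protocol and SAP*

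**What the plan says.** Two sections describe the review that closes a dose cohort.

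- Section 3.0: the SMC meets when a cohort is finalised, meaning that "three patients has completed minimum 8 weeks of treatment".
- Section 9.8: "the SMC will meet after every time three patients have completed each dose level (i.e. completed the re-radiation". The stated purpose is to judge whether moving up a level is safe, and "No further patients will be included until the SMC has met".

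Section 3.0 sends the reader to the dose-limiting toxicity (DLT) section for definitions (cited as 8.8, now 9.8). That section gives the other trigger, so the cross-reference does not settle the matter.

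The calendar comes from three places.

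- Section 5.2: nivolumab is given every 2 weeks, "starting two weeks (Cycle 1, Day 1) before start of radiotherapy". Within escalation, "the subsequent patient will start therapy with nivolumab 6 weeks after the previous to allow time to observe the possibility for acute toxicity". All patients go to 3.0 mg/kg at Cycle 5 Day 1, which 5.2 places 2 weeks after the end of RT. After escalation, "The remaining patients will be treated at the maximum tolerated dose".
- Table 1 (section 5.2.1): RT is given "5 days a week, 4 weeks (Cycle 2 and 3".
- Section 2.3: the expectation is that "any increased toxicity will be observed within 2 weeks after end of RT and thus allow for a 3.0 mg/kg Q2W dose level thereafter".

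**The concern.** Section 2.3 puts the main risk in RT inflammation made worse by PD-1 blockade, and 9.8 foresees severe dermatitis and mucositis. The weeks just after RT are therefore the ones the escalation decision most needs to see. Section 9.8 has rules for Grade 3 and Grade 4 events but gives no DLT observation period, and 5.2 escalates if no DLT has been observed. For the third patient in a cohort, the SMC trigger is in effect the observation window, and the protocol gives two values for it.

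A team that follows 9.8 can clear 1.0 mg/kg with none of the third patient's 2 post-RT weeks on record. The same trigger is used a second time before expansion, which is 20 - 6 = 14 patients if no patients are added during escalation. Section 5.2 states the 6-week stagger only for the escalation part.

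**Working it through.** **Inputs.** Lead-in of 14 days; 60 Gy at 1.5 Gy twice daily, 5 days a week; stagger of 42 days between nivolumab starts (5.2, Table 1). Post-RT window of 14 days (2.3). Triggers from 3.0 and 9.8. Day 0 is a patient's first nivolumab dose.

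**1. The plan's own figure.** 60 / (2 x 1.5) = 20 treatment days, and 20 / 5 = 4 weeks. Lead-in + RT + window = 14 + 28 + 14 = 56 days. Cycle 5 Day 1 is 4 x 14 = day 56, which is 8 weeks. So the 8 weeks in 3.0 equal the nominal end of the window in 2.3.

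**2. Third patient, no missed RT days.** With RT starting on day 14, the twentieth treatment day L is day 39 for a Monday start and day 41 for a Tuesday to Friday start. The window closes at L + 14.

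| | Monday start | Tuesday to Friday start |
|---|---|---|
| Last fraction, earliest 9.8 trigger | day 39 | day 41 |
| Window closes | day 53 | day 55 |
| 3.0 trigger | day 56 | day 56 |
| 3.0 minus 9.8 | 17 days | 15 days |

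With one missed day L = 42, and the difference is 56 - 42 = 14 days.

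**3. Earliest trial calendar, with no SMC or inclusion lag.** Patients 1 to 3 start at weeks 0, 6 and 12.

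- 9.8: first 3.0 mg/kg dose at 12 + 6 = week 18; patients 5 and 6 at weeks 24 and 30; expansion at 30 + 6 = week 36.
- 3.0: first 3.0 mg/kg dose at 12 + 8 = week 20; patients 5 and 6 at weeks 26 and 32; expansion at 32 + 8 = week 40.

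At week 18 the windows of patients 1 and 2 have closed (weeks 8 and 14), and patient 3's is open. Patient 4's first dose would fall on patient 3's day 42, with 53 - 42 = 11 or 55 - 42 = 13 window days still to come.

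**4. Patient 4's RT.** It starts at 42 + 14 = day 56 of patient 3, which is 1 to 3 days after the window closes. Even without the stagger, a start on day L puts RT at L + 14, no earlier than closure.

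**5. The 3.0 trigger when RT overruns.** The documents give no make-up rule. Assume missed days are added on later weekdays.

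| Missed RT days | Last fraction | Window closes | Unobserved at day 56 | RT-to-RT gap to next patient (56 - L) |
|---|---|---|---|---|
| 0 | 39 to 41 | 53 to 55 | 0 | 15 to 17 days |
| 1 | 42 | 56 | 0 | 14 days |
| 2 | 43 to 45 | 57 to 59 | 1 to 3 days | 11 to 13 days |
| 5 | 46 to 48 | 60 to 62 | 4 to 6 days | 8 to 10 days |

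The 8-week wording is therefore also not fully safe when RT overruns.

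**The case against.** The two triggers can be reconciled: on the planned schedule a review at 8 weeks satisfies both sections. Cohort dosing also runs to the end of Cycle 4, because everyone moves to 3.0 mg/kg at Cycle 5, and this fits the 3.0 reading of a finished cohort. During patient 3's open window, patient 4 receives nivolumab without RT, and 2.3 describes the 3.0 mg/kg dose as mild in monotherapy and tolerance as good up to 10 mg/kg. Toxicity assessment is continuous (8.1.2.1), and a late event still triggers the 9.8 rules. Expansion raises no dose and has its own stop: inclusion halts for an SMC meeting after two Grade 3 events or one Grade 4 event related to nivolumab.

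Most of this stands, and it is why the point is minor. It does not remove the conflict. The protocol does not tell the team to use the later trigger, and an infused dose cannot be taken back.

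A reader might infer that patients could receive the higher-dose combination with RT before the previous cohort's window closes. Step 4 of the working shows that the planned schedule prevents this.

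A reader might also infer that the 6-week stagger breaks a promised 2-week post-RT separation between patients. It does not. Section 5.2 offers only time to observe acute toxicity. The window in 2.3 was written for the step to 3.0 mg/kg within one patient. The four within-cohort steps are at the same dose, and the shortfall at two missed days is 1 to 3 days under an assumed make-up rule.

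**Conclusion.** The conflict between 3.0 and 9.8 is real and unresolved in the text. Its size is about 2 weeks per cohort (14 to 17 days with 0 or 1 missed RT day): the earliest 3.0 mg/kg dose moves from week 20 to week 18, and the earliest expansion from week 40 to week 36. At the 9.8 trigger one of the cohort's three post-RT windows can be wholly unobserved. What is affected is the basis of the SMC decision and the first higher nivolumab dose.

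The calendar assumes that the SMC meets and the next patient is dosed with no lag; each day of lag shrinks the gap. It also assumes that RT keeps to its planned 2 weeks after nivolumab start. The documents give no frequency of missed RT days, so the overrun figures are arithmetic and not expected exposure. Figure 1, to which 5.2 refers for the escalation schedule, is not shown and might clarify the timing. Confidence is medium, and the level is consider.

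**What to change.** Use one trigger in both 3.0 and 9.8, for example:

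*The SMC reviews a dose level when three patients have completed a minimum of 8 weeks of treatment and at least 2 weeks have passed since each patient's last RT fraction; no patient is included at the next level or in the expansion before this review.*

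The second condition closes the overrun gap left by the present 3.0 wording.

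**Cost.** No added patients, visits or procedures. Against 3.0: no delay with 0 or 1 missed RT day, 1 to 3 days with two, and 4 to 6 days with five. Against 9.8: about 2 weeks per cohort, or 2 x 2 = 4 weeks before expansion. The enrolment period, taken as 1 April 2017 to 31 December 2018, is 639 / 7 = about 91 weeks.

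**Optional remark on 5.2.** The sponsor could add that the next escalation patient does not start nivolumab before the previous patient's actual last RT fraction. With 0 or 1 missed day this changes nothing. With two it adds 1 to 3 days. It would not guarantee a 14-day gap if Cycle 2 Day 1 and RT were both brought forward by 3 days (14 - 3 = 11 days), and the protocol does not require that gap.

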5.2.1 Study drug

The product storage manager at the local pharmacy should ensure that the study drug is stored in accordance with the environmental conditions (temperature, light, and humidity) as determined by BMS. If concerns regarding the quality or appearance of the study drug arise, the study drug should not be dispensed and contact BMS immediately.

Investigational product documentation must be maintained. That includes all processes required to ensure drug is accurately administered. This includes documentation of drug storage,

administration and, as applicable, storage temperatures, reconstitution, and use of required processes (eg, required diluents, administration sets).

Infusion-related supplies (eg, IV bags, in-line filters, 0.9% sodium chloride injection, 5% dextrose injection) will not be supplied by the sponsor and should be purchased locally if permitted by local regulations.

The investigational product should be stored in a secure area according to local regulations. It is the responsibility of the investigator to ensure that investigational product is only dispensed to study subjects. The investigational product must be dispensed only from official study sites by authorized personnel according to local regulations.

[figure not shown]
Please refer to the current version of the Investigator Brochure (IB) and/or pharmacy reference sheets for complete storage, handling, dispensing, and infusion information for nivolumab.

The infusion will be administered by nurses with experience in treatment with immunotherapy.

Table 1 Study Treatment

Drug	Dose/Potency	Dose Frequency	Route of Administration	Regimen/Treatment Period	Use
Nivolumab	1,0 mg/kg	Q2W	IV infusion	Day 1 of each 2 week cycle	Experimental, Dose level 1
Nivolumab	3,0 mg/kg	Q2W	IV infusion	Day 1 of each 2 week cycle	Experimental, Dose level 2
Radiotherapy	1,5 Gy	BID		5 days a week, 4 weeks (Cycle 2 and 3)	Standard

Figure 1

5.3 Dose schedule and modification

5.3.1 Nivolumab Schedule

Continuation of nivolumab treatment with suspected progression is permitted, see Section 5.3.2.4. Treatment will continue for a maximum of 12 months, or discontinuation from study treatment due to any of the criteria listed in section 5.5.

If required, subjects may receive nivolumab up to 3 days before or after the scheduled date. A dose given more than 3 days after the intended dose date will be considered a delay. Subsequent dosing should be based on the actual date of administration of the previous dose of drug.

Subjects should be monitored for infusion reactions during nivolumab administration. If an acute reaction is noted, subjects should be managed according to Section 5.3.2.6. Doses of nivolumab may be interrupted, delayed or discontinued as needed.

5.3.2 Dose Modifications for Nivolumab

Dose modification is only allowed in case of Dose Limited Toxicity (DLT). See section 8.8 for instructions. For dose delay, see 5.3.2.1

5.3.2.1 Dose Delay Criteria for Nivolumab

Dose delay criteria apply for all drug-related AEs. A treatment delay up to 4 weeks, i.e. 6 weeks calculated from the last dose, is allowed. A treatment delay beyond this must be discussed with the Study leadership. A treatment delay beyond 10 weeks is not allowed.

Tumor assessments should continue per protocol schedule, even if dosing is delayed.

Nivolumab administration should be delayed for the following reasons:

- Any Grade ≥ 2 non-skin drug-related adverse event, except for fatigue and laboratory abnormalities
- Any Grade 3 skin drug-related adverse event
- Any Grade 3 drug-related laboratory abnormality
- Any adverse event, laboratory abnormality, intercurrent illness or other reason which, in the judgment of the investigator, warrants delaying the dose of study medication.

Subjects who require delay of nivolumab should be re-evaluated weekly or more frequently if clinically indicated. Nivolumab dosing can be resumed on the established dosing schedule when retreatment criteria are met (Section 5.3.2.2).

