5.3.2.3 Treatment Discontinuation Criteria for Nivolumab

Nivolumab treatment should be permanently discontinued for the following:

- Any grade 4 drug-related toxicity
- Any Grade 2 drug-related uveitis, eye pain or blurred vision that does not respond to topical therapy and does not improve to Grade 1 severity within the re-treatment period OR requires systemic treatment.
- Any Grade 3 non-skin, drug-related adverse event lasting > 7 days, with the following exceptions for laboratory abnormalities, drug-related uveitis, pneumonitis, bronchospasm, hypersensitivity reactions, infusion reactions, and endocrinopathies:
 - Grade 3 drug-related uveitis, pneumonitis, bronchospasm, hypersensitivity reaction, or infusion reaction of any duration requires discontinuation
 - Grade 3 drug-related endocrinopathies adequately controlled with only physiologic hormone replacement do not require discontinuation
 - Grade 3 drug-related laboratory abnormalities do not require treatment discontinuation except:
 - Grade 3 drug-related thrombocytopenia > 7 days or associated with bleeding requires discontinuation
- Any drug-related liver function test (LFT) abnormality that meets the following criteria require discontinuation:
 - AST or ALT > 5 x ULN for 2 weeks
 - AST or ALT > 5 x ULN
 - Total bilirubin > 3 x ULN
- Any Grade 4 drug-related adverse event or laboratory abnormality, except for the following events which do not require discontinuation:
 - Grade 4 neutropenia ≤ 7 days
 - Grade 4 lymphopenia or leukopenia
 - Isolated Grade 4 amylase or lipase abnormalities that is not associated with symptoms or clinical manifestations of pancreatitis. The Study leadership should be consulted for Grade 4 amylase or lipase abnormalities.
 - Isolated Grade 4 electrolyte imbalances/abnormalities that are not associated with clinical sequelae and are corrected with supplementation/appropriate management within 72 hours of their onset
 - Grade 4 drug-related endocrinopathy adverse events, such as adrenal insufficiency, ACTH deficiency, hyper- or hypothyroidism, or glucose intolerance, which resolve or are adequately controlled with physiologic hormone replacement (corticosteroids, thyroid hormones) or glucose-controlling agents, respectively, may not require discontinuation after discussion with and approval from the Study leadership.
- Any event that leads to delay in dosing lasting > 6 weeks from the previous dose requires discontinuation, with the following exceptions:

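### For a drug-related adverse event managed without a steroid taper, a delay of more than 6 weeks from the last dose calls for discussion under section 5.3.2.1 but permanent discontinuation under section 5.3.2.3

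*Combined protocol and SAP*

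**What the plan says.** Section 5.3.1 defines lateness: "A dose given more than 3 days after the intended dose date will be considered a delay". It ends treatment at 12 months or on "discontinuation from study treatment due to any of the criteria listed in section 5.5". Section 5.5 in turn makes discontinuation obligatory for the adverse events described in 5.3.2.3.

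Section 5.3.2 sends the reader with a question about delay to 5.3.2.1, which sets three steps:

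- Scope: "Dose delay criteria apply for all drug-related AEs".
- Tolerated delay: "A treatment delay up to 4 weeks, i.e. 6 weeks calculated from the last dose, is allowed".
- Longer delays: "A treatment delay beyond this must be discussed with the Study leadership", with an outer limit, "A treatment delay beyond 10 weeks is not allowed".

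Section 5.3.2.1 refers to 5.3.2.2 for the conditions on restarting. It does not refer to 5.3.2.3.

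Section 5.3.2.3 lists reasons for permanent discontinuation. One of them is: "Any event that leads to delay in dosing lasting > 6 weeks from the previous dose requires discontinuation, with the following exceptions". The exceptions are delays for prolonged steroid tapers given for drug-related events, and delays for reasons unrelated to the drug that the Study leadership approves. The section also requires consultation with the Study leadership before any restart after more than 6 weeks.

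**The concern.** Take a patient whose drug-related adverse event resolves slowly and is managed without a steroid taper. An investigator who goes from 5.3.2 to 5.3.2.1 finds a duty to discuss and an outer limit, and can reasonably infer that dosing may resume in between. An investigator who goes from 5.3.1 through 5.5 to 5.3.2.3 must stop the drug for good. Both have followed the protocol's own cross-references.

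What is at stake is patient safety and uniform treatment in a trial whose primary objectives are safety, tolerability and a safe dose. Section 9.8 foresees Grade 3 or 4 dermatitis and mucositis. When such events are drug-related, other rules in 5.3.2.3 already stop nivolumab for Grade 4 events and for Grade 3 mucositis lasting more than 7 days. Of the events that 9.8 names, this leaves mainly Grade 3 dermatitis to the delay rule. "Any Grade 3 skin drug-related adverse event" is a reason to delay, and skin events fall outside the 7-day stopping rule for Grade 3 events. Grade 2 non-skin events, apart from fatigue and laboratory abnormalities, also trigger a delay, although 9.8 does not name them.

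**Working it through.** **Inputs.** Dosing every 2 weeks (5.2). Tolerated delay of 4 weeks, equated with 6 weeks from the last dose, and outer limit of 10 weeks (5.3.2.1). Discontinuation beyond 6 weeks from the previous dose (5.3.2.3). Delay counted from the intended dose date (5.3.1).

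**Step 1: reproduce the protocol's own figure.** Time from last dose = dosing interval + delay = 2 + 4 = 6 weeks. This matches the equivalence stated in 5.3.2.1, so the two sections turn on the same point in time.

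**Step 2: set the rules side by side for a drug-related event without a steroid taper.**

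| Time from last dose | 5.3.2.1 | 5.3.2.3 |
|---|---|---|
| Up to 6 weeks | Delay allowed | No discontinuation for delay alone |
| More than 6 weeks, up to the outer limit | Discuss with the Study leadership | Discontinue permanently; neither exception applies |
| Beyond the outer limit | Not allowed | Discontinue permanently |

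The sections differ only in the middle row.

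**Step 3: length of the middle row.** The text does not say when the 10 weeks start.

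- From the intended dose date, which is how 5.3.1 and the 4-week figure count: 2 + 10 = 12 weeks from the last dose. The window is 12 − 6 = 6 weeks. On the two-week schedule it holds the dose days at weeks 8, 10 and 12, so 3.
- From the last dose: the limit is 10 weeks. The window is 10 − 6 = 4 weeks, with dose days at weeks 8 and 10, so 2.

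**Step 4: what the choice means for one patient.** This is an illustration under assumed inputs: 26 planned doses at weeks 0, 2, …, 50 from the first dose, last dose before the hold at Cycle 4 Day 1 (week 6), no progression, and no further interruption.

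- Discontinuation under 5.3.2.3: 0 further doses.
- Restart 8 weeks after the last dose (week 14): (50 − 14)/2 + 1 = 19 doses.
- Restart 10 weeks after (week 16): (50 − 16)/2 + 1 = 18 doses.
- Restart 12 weeks after (week 18): (50 − 18)/2 + 1 = 17 doses.

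The contrast is therefore 0 against 17 to 19 doses with the 12-week limit, or 0 against 18 to 19 with the 10-week limit. Progression or a second hold would lower the larger figures, so they are close to a maximum.

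**Step 5: the steroid-taper exception.** Section 5.3.2.3 lifts the 6-week stop for tapers and gives no maximum. The limit in 5.3.2.1 covers drug-related events, and tapers treat such events. A taper delay that ends before the limit satisfies both sections. The cross-reference is missing, but the rules do not collide.

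**The case against.** The strongest reply is that the sections can be read together: up to 6 weeks the delay is allowed; after that the drug stops unless an exception in 5.3.2.3 applies, following discussion; past the outer limit it never restarts. Section 5.3.2.1 does not say in terms that dosing may resume after 6 weeks. The discussion step would still serve taper cases and delays for intercurrent illness or other reasons. Section 5.5 uses the firmest wording and points to the conservative rule.

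This is a sensible reading and may be what was meant, but no sentence states it. Section 5.3.2.1 gives its own scope and its own ceiling without mentioning the exceptions. For the patient considered here, the discussion would have nothing to decide. The consultation required by 5.3.2.3 is a condition on restarting where restarting is permitted; it does not create a further exception.

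Two limits on reach do stand. Dermatitis attributed to radiotherapy and not to nivolumab is unrelated to the drug and can be handled under the approved exception, so the conflict does not arise. Restarting also needs recovery under 5.3.2.2, generally to Grade 1 or baseline. A reader might infer that patients could be re-exposed with no safeguard. The recovery criteria and the consultation step do not support that inference.

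**Conclusion.** The inconsistency is real and should be corrected. For a drug-related event without a steroid taper, the protocol gives two different instructions from just over 6 weeks to either 12 or 10 weeks from the last dose, covering 3 or 2 scheduled dose days. The 12-week figure rests on the protocol's own use of *delay*; the 10-week figure is the alternative that the text leaves open. The documents do not give the number of patients affected; it is probably few of 20. The gain is consistent handling of slowly resolving toxicity.

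Two stronger conclusions may tempt a reader. The first is that the taper exception contradicts the 10-week limit. It does not, since both can be obeyed up to that limit. The second is that the trial's results are compromised. The analysis is descriptive, and no planned statistical figure changes.

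**What to change.** In 5.3.2.1, replace the sentence on discussion with: *A delay of more than 6 weeks from the last dose requires permanent discontinuation, except under the exceptions in 5.3.2.3 and after consultation with the Study leadership.* If discretion is intended for all drug-related adverse events, add it to 5.3.2.3 as a third exception instead, so that both sections say the same thing.

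As a separate clarification, add to the steroid-taper exception in 5.3.2.3 that the 10-week limit of 5.3.2.1 applies to drug-related delays. The sponsor should state whether that limit runs from the intended dose date or from the last dose; the review should not choose for them. Leave the exception for approved delays unrelated to the drug unchanged, because capping it would be a new policy.

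The cost is protocol wording in two sections. Under the stricter rule, a few patients with slowly resolving toxicity not treated with steroids may stop nivolumab earlier, and a taper that runs past the limit would end treatment.
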